- 4.8 **Identification of participants for patient-reported outcome surveys.** All eligible patients who speak English or Spanish will be invited to participate in a survey of patient-reported outcomes. We will confirm if the potential participant has an active email address via our membership databases. Those who do will be initially contacted via email; those who do not will be initially contacted via postal mail (see contact workflow descriptions, below). Those who agree to participate will be asked to complete these two brief surveys at 3 time points (3-, 6- and 12-months). We will alert the oncology teams at all participating medical centers, as well as KPSC Member Services, in advance so that they are aware of the survey administration schedule and prepared to address any patient questions about the surveys and/or the study.
- 4.9 **Survey administration and tracking:** We will use RedCap software for all recruitment and survey tracking, as well as for on-line consenting and administration of the surveys whenever possible (e.g., for all patients with a viable email address), as well as for tracking postal mail and phone recruitment contact attempts.
- 4.10 **Outcomes:**

Primary. Our primary outcome is percent of eligible patients screened and referred (based on PHQ score) at intervention versus control sites.

Secondary. Our secondary outcomes include: completion of recommended referrals, utilization of outpatient medical oncology visits, primary care visits, behavioral health visits, urgent care visits, and emergency department visits; we will also examine patient-reported outcomes using the Functional Assessment of Cancer Therapy-Breast survey, and the Breast Cancer Prevention Trial (BCPT) Symptom Checklist.

***Please note: We received a waiver of written informed consent for the electronic health record data collection aspect of the study to identify newly diagnosed breast cancer patients at intervention and control sites during the screening intervention period (12 months) on September 22, 2016; we received a waiver of written informed consent for the survey portion of the study on May 8, 2017.***

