## **5.0 DATA SOURCES**

We will obtain and compare data from the sources described below for patients from both the intervention and the control condition.

- 5.1 Distress screening: We will use a recommended distress screening instrument (PHQ), which is part of the electronic health record.
- 5.2 Referral: We will access referral data using Tapestry, a database linked to the KPSC electronic medical record that records all referral activities, including those to behavioral health services. We will collect referral data retrospectively at completion of the 12 month screening intervention. We will collect and compare the number of referrals to relevant behavioral health services, including: depression care management, psychiatry, psychology, social work, and health education. We will also obtain information on referral initiation and completion (e.g., patient visit with referred provider).
- 5.3 Utilization of health care services: To compare patient utilization of health services between intervention and control sites, we will capture utilization of health services from our electronic medical record using Current Procedural Terminology (CPT) and International Classification of Disease (ICD) codes as appropriate. We will collect utilization data retrospectively at 18 months after the initiation of the distress screening program in the intervention centers. This will provide utilization data for a maximum of 18 months. We will capture number of emergency department visits, hospitalizations, urgent care visits, primary care and oncology visits, and behavioral health visits, including interactions with psychology, psychiatry, and social workers (in-person, email, and telephone contact).
- 5.4 Covariates and breast cancer treatment data: We will collect covariate information from the electronic health record and data from the KPSC tumor registry. Covariates from the registry will include date of diagnosis, age at diagnosis, stage of disease, estrogen receptor/progesterone receptor/human epidermal growth factor receptor 2 status, treatment types and dates including use of Herceptin and aromatase inhibitors, laterality, tumor size and histology, sequence number, and treating medical center. Covariates from the electronic record will include age, date of birth, gender, race/ethnicity, and geocoded census tract education and income.

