#### **14.0 STATISTICAL CONSIDERATIONS**

**Aim 1: Evaluate the effectiveness of a guideline-recommended distress screening program for breast cancer patients in improving identification of distressed patients, initiation and completion of referrals to behavioral health, and patient-reported and utilization outcomes as compared to usual care within KPSC, using a pragmatic cluster randomized control trial design.**

- 14.1 **Power and sample size.** Of the 14 KPSC medical centers, we have selected 6 centers with the highest average number of new breast cancer cases diagnosed between 2011 and 2014. Based on the average number of cases. We expect a total of at least 1,200 newly diagnosed patients across the 6 sites, and to enroll anywhere from 50 to 300 newly diagnosed breast cancer patients per intervention site, entering all such cases into our cohort with no exclusions. We performed cluster randomization to select the intervention and control sites. While cluster randomization may be less statistically efficient than individual randomization, we believe it makes the study more feasible for several reasons. First, it allows us to truly evaluate the effectiveness of the distress screening program, with the screening offered to all newly diagnosed patients in the intervention centers. This will provide real-world information on uptake and effectiveness. Second, it allows us to avoid contamination between the distress screening intervention and other possible competing interventions, as well as outside information that may be publicly available to patients. Third, it allows us to balance (on average) medical center-level factors that we are otherwise unable to measure reliably. For all outcomes, we expect relatively small standardized effect sizes (measured in terms of z-scores) ranging from 0.2-0.4, because this is an effectiveness study. To achieve 80% power with a significance level of 0.05, our per-center sample size requirement ranges from as few as 20 for large effect size (0.4) and zero intraclass correlation (ICC), to about 400 for small effect size

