and large ICC (0.2 and 0.01, respectively). Given that we can expect 50 to 300 newly diagnosed breast cancer patients per center, we should be adequately powered to detect effect sizes as small as 0.2, given ICCs no greater than 0.007. This is a lower bound on our power, since we expect to have as many as 200 more patients at some medical centers, and so our power is most likely greater than reported here.

- 14.2 Statistical analysis plan: All variables will be described with summary statistics appropriate for measurement type, such as frequency and percent, mean, median, standard deviation, minimum, and maximum. Patterns of missing values will be examined and evaluated for randomness using the method described by Enders. Diagnostic plots and inferential tests for tenability of assumptions will be evaluated for our primary and secondary outcomes, and appropriate remedial methods (e.g., Box-Cox transformations) applied where required. We will analyze referral and utilization outcomes as the total amount of services used during the study period, and use said diagnostic tests to determine the best modeling strategy for examining relationships with relevant demographic and clinical characteristics, exploring potential disparities by race/ethnicity and socioeconomic status. If necessary, we will analyze relationships with referral and utilization outcomes using Poisson or Negative Binomial regression models. We will use an intent-to-treat analysis, including data on all newly diagnosed patients in the intervention and control groups without regard to their screening status, appropriate for a cluster RCT.

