Patient-reported outcomes from our mailed patient surveys (FACT B and BCPT) will be subjected to the same diagnostic testing as the utilization outcomes. To account for having repeated measurements for these patient-reported outcomes (3, 6, and 12 months post-diagnosis), we will use generalized estimating equations or linear mixed effects models, for situations where no or some repeated measures are missing, respectively. We will also analyze patient-reported outcomes using non-parametric regression techniques, such as quantile regression, to assess the sensitivity of our findings to other key modeling assumptions. Additionally, to analyze any improvement in identification of highly distressed patients by the systematic screening program, we will compare patients reporting high levels of distress on the FACT-B with patients receiving referral for high-level distress services (psychiatry, psychology). Statistical analyses will be conducted using SAS, R and/or MPlus. The study team will meet regularly to review adherence to the study protocol, evaluate study progress, and identify and resolve issues. Frequencies tables will be examined and out-of-range checks of all variables will be conducted, and results checked for consistency. Our advocate and advisors will provide insights and suggestions to guide our analyses to ensure we are considering a broad range of views

**Aim 2: Identify patient-, clinician-, and system-level barriers and facilitators to implementation of the program, and assess stakeholder-perceived acceptability, fidelity, and achievements of the program**

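### Section 14.2 ties no model or test to medical centre, the unit of randomisation (3 v 3), and names no analysis for the primary outcome; if centre were left out, a nominal 5% comparison could have a type I error of 21% to 26% at the non-zero ICCs in 14.1

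*Combined protocol and SAP*

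**What the plan says.** Sections 3.0 and 8.0 make the medical centre the unit of randomisation, with three intervention and three control centres. Section 3.0 anticipates 1,200 patients, 600 per arm. Section 14.1 expects 50 to 300 patients per centre and effects of 0.2 to 0.4 SD. It works with an ICC of zero, of 0.007 (the limit for its power claim at effect 0.2) and of 0.01 (its large case). The level is given as "To achieve 80% power with a significance level of 0.05", without sides.

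The analysis provisions are these:

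- **Primary outcome (4.10):** "Our primary outcome is percent of eligible patients screened and referred (based on PHQ score) at intervention versus control sites". Section 14.2 names no test or model for this percentage. It treats referral only as a total amount of services.
- **Referral and utilisation totals (14.2):** diagnostics will be used to "determine the best modeling strategy for examining relationships with relevant demographic and clinical characteristics". Then: "If necessary, we will analyze relationships with referral and utilization outcomes using Poisson or Negative Binomial regression models".
- **Survey scores (14.2):** "To account for having repeated measurements for these patient-reported outcomes (3, 6, and 12 months post-diagnosis), we will use generalized estimating equations", or linear mixed models. As a sensitivity analysis, "We will also analyze patient-reported outcomes using non-parametric regression techniques, such as quantile regression".
- **Identification of distress (14.2):** high distress on the FACT-B is compared with referral to high-level services. No method is given.
- **Population (14.2):** intent to treat, "including data on all newly diagnosed patients in the intervention and control groups without regard to their screening status, appropriate for a cluster RCT".
- **Covariates (5.4):** the registry list ends "tumor size and histology, sequence number, and treating medical center". Nothing assigns centre to a model.

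**The concern.** Patients in one centre share staff, workflow and referral resources. Section 4.5 lets the screening workflow vary by site, and section 4.7 makes the social-work pathway depend on whether the site has that resource. The information about the arm effect therefore comes from six centres, and the sample size section recognises this by using an ICC. The analysis section does not follow through. The repeated-measures models are justified by correlation within a patient, and the count models carry no cluster term. The one reference to a cluster trial describes who is analysed and not how variance is estimated.

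If centre is left out, ordinary differences between six centres can be reported as an effect of screening, with intervals that are too narrow. Because no analysis is fixed for the primary outcome, a valid and an invalid method are both compatible with the plan as written.

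**Working it through.** **Inputs.** Three centres per arm (3.0); mean centre size m = 600/3 = 200 (3.0); ICC 0, 0.007 and 0.01 (14.1); level 0.05 (14.1), taken both two-sided and one-sided because the sides are not stated; effects 0.2 and 0.4 (14.1).

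**The plan's own figures.** Section 14.1 gives 20 per centre (effect 0.4, ICC 0) to about 400 (effect 0.2, ICC 0.01) for 80% power. The usual formula is n0 = 2(z_alpha + 0.842)²/d² per arm, with per-centre size n0(1 − ICC)/(3 − n0·ICC).

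- Effect 0.4, ICC 0: n0 = 98.1, so 98.1/3 = 32.7, or 33 per centre (one-sided 77.3/3 = 25.8, or 26).
- Effect 0.2, ICC 0.01: n0·ICC = 3.92 (one-sided 3.09). Both exceed 3, so no centre size reaches 80%.

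The stated range is therefore not reproduced with three centres per arm. That is a separate matter; the steps below use only the plan's ICCs, effects and mean centre size.

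**Type I error if centre is left out.** Design effect DE = 1 + (m − 1)·ICC. Two-sided error = 2[1 − Φ(1.960/√DE)]; one-sided error = 1 − Φ(1.645/√DE).

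| ICC | DE | Two-sided | One-sided |
|---|---|---|---|
| 0 | 1 | 5.0% | 5.0% |
| 0.001 (assumed) | 1 + 199 × 0.001 = 1.199 | 7.3% | 6.7% |
| 0.007 | 1 + 199 × 0.007 = 2.393 | 20.5% | 14.4% |
| 0.01 | 1 + 199 × 0.01 = 2.990 | 25.7% | 17.1% |

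Simulation of a percentage outcome (beta-binomial, prevalence 0.1 to 0.5, 40,000 null trials per setting) gave 20.4% to 21.4% at ICC 0.007 and 25.5% to 26.5% at 0.01. A t-test on six centre proportions stayed at 4.8% to 5.2%.

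**Centre size.** With every centre at 50, the two-sided error is 9.1% (ICC 0.007) and 10.8% (0.01); with every centre at 300 it is 26.5% and 32.7%. These are illustrations only, since they imply 300 and 1,800 patients. With assumed centres of 50, 150, 200, 200, 300 and 300 (total 1,200), a percentage outcome gives 22% to 23% and 27% to 28%, while the centre t-test stays at 4% to 5%.

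**Large-sample adjustment is not enough.** With six equal centres and a two-sided 1.96 cut-off:

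- unbiased between-centre variance: 2·P(t4 > 1.960) = 12.2%;
- uncorrected robust variance: 2·P(t4 > 1.960·√(2/3)) = 18.5%.

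**Fixed centre effects.** An intercept, an arm term and five centre indicators form a matrix of rank 6 with 7 columns, so arm cannot be separated from centre.

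**Permutation.** There are C(6,3) = 20 allocations. The smallest p is 2/20 = 0.10 two-sided and 1/20 = 0.05 one-sided.

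**Power of a valid test.** Centre-summary t-test, 4 df, SE = √(2·DE/(3·200)), non-central t:

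| ICC | SE | Effect 0.2, two-sided | Effect 0.2, one-sided | Effect 0.4, two-sided |
|---|---|---|---|---|
| 0 | 0.0577 | 74% | 88.0% | above 99% |
| 0.007 | 0.0893 | 40% | 58.1% | 91% |
| 0.01 | 0.0998 | 34% | 50.5% | 84% |

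**The case against.** The strongest reply is that no arm comparison ignoring centre is actually prescribed. The count models are introduced for relationships with patient characteristics, and only if needed. GEE and mixed models can carry a centre level. Section 14.1 uses an ICC and concedes a loss of efficiency, so the authors clearly know that the design is clustered. All of this stands. A reader might infer that the plan intends to ignore centre, or that the trial will have a 21% to 26% error rate. The documents support neither reading: they are silent on the analysis, and the figures are conditional on centre being left out.

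Nor do the documents predict an ICC of 0.007 or 0.01. Section 14.1 also uses zero, where there is no inflation. The first non-zero value is a limit for adequate power and the second is the plan's large case. Equally, no ICC is forecast for any outcome, so nothing in the plan justifies treating clustering as negligible.

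It may also be said that any competent analyst would adjust. With six clusters the form of adjustment decides validity, as the 12% and 18% results show. A general intention to adjust would not settle the matter.

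Finally, several small-sample methods are valid. Insisting on a t-test of centre summaries alone would be a preference and not a requirement.

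**Conclusion.** The omission is real and should be closed before the arm comparisons are made. Section 14.2 links no model or test to the randomised unit and gives no analysis for the primary outcome. At 200 patients per centre, the consequence of leaving centre out runs from none at ICC 0 to about four times (0.007) and five times (0.01) the nominal two-sided 5% level; one-sided, it is about three times at both.

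These sizes rest on equal centres at the planned mean and on the ICCs in 14.1. They apply to outcomes taken from the medical record. Surveys are voluntary and limited to English and Spanish speakers, so responders per centre will be fewer and the inflation smaller, by an amount the documents do not give. Unequal centres raise it slightly. Listing centre as a covariate does not fill the gap, because as a fixed effect it is confounded with arm.

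**What to change.** State in 14.2 that every arm comparison, including the primary, is made at the level of randomisation with a few-cluster method on about 4 df, and say whether tests are one- or two-sided. Any of these forms would do:

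- a t-test on six centre summaries (proportions, log rates or means), which may first be adjusted for patient covariates;
- a mixed model with a random centre intercept and small-sample df. It is conservative if the centre variance is truncated at zero: simulated two-sided type I error was 0.4% at ICC 0, 2.6% at 0.007 and about 3% at 0.01;
- GEE clustered on centre, with a small-sample-corrected variance and a t reference.

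For survey scores, nest repeated measures in patient within centre. Rule out centre as a fixed effect in arm comparisons, a large-sample z reference, and a permutation test as the only analysis. State the resulting power beside the chosen method.

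The cost is wording and analysis work, with no new data. At 200 per centre, valid two-sided 95% intervals are 2.776·√DE/1.960 = 2.2 times (ICC 0.007) to 2.4 times (0.01) as wide as those that leave centre out. Clustering itself contributes √DE = 1.5 to 1.7 of that, and 4 df contributes 2.776/1.960 = 1.4. The stated power falls to the values tabulated above; with the assumed unequal centres it is 62%, 36% and 31% (two-sided, effect 0.2) at ICC 0, 0.007 and 0.01. Part of the shortfall from 80% belongs to the design and not to this change: even with a normal reference, two-sided power at effect 0.2 is only 61% at ICC 0.007 and 52% at 0.01.

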## **15.0 REGISTRATION GUIDELINE**

In this pragmatic cluster randomized trial, randomization is at the medical center level. We will not recruit or consent patients individually; those at intervention sites will be offered the distress screening program as part of usual clinical care, and we have been granted a waiver of written informed consent from the IRB.

## **16.0 BIOHAZARD COMTAINMENT**

This section is not applicable. No biological samples will be collected.

## **17.0 ETHICAL AND REGULATORY CONSIDERATIONS**

All institutional and Federal regulations concerning the Informed Consent form for patient surveys will be fulfilled. The study will be conducted in adherence to ICH Good Clinical Practice.

